Date: 12/29/2022

Version Number: 13

Principal Investigator: [name] [name]

Application Number: 2014239

Application Title: The Impact of Insomnia Treatment on Heavy Alcohol use among Returning Veterans (Project iTAP for Veterans)

Protocol

1. Abstract

Heavy alcohol use is prevalent among returning Veterans and results in significant physical and psychological burden. One in five returning Veterans screens positive for probable past-year alcohol use disorder (AUD), and few hold positive beliefs about mental health treatment. Moreover, brief interventions for alcohol use demonstrate limited efficacy within this population. Thus, additional strategies are needed to engage and treat returning Veterans who may be at risk for AUD. More than half of returning Veterans who screen positive for hazardous drinking report clinically significant symptoms of insomnia. In turn, insomnia symptoms have been associated with increased risk of alcohol-related problems, perhaps due to insomnia-related impairments in executive functioning, negative emotionality, craving for alcohol, and use of alcohol as a sleep aid. The proposed K23 aims to determine the utility of the first line of treatment for insomnia (Cognitive Behavioral Therapy for Insomnia or CBT-I) in reducing alcohol use and related problems among Veterans of the Operation Enduring Freedom (OEF), Operation Iraqi Freedom (OIF), and Operation New Dawn (OND) era. Forty-four Veterans who report heavy drinking ($\geq 4/5$ drinks per occasion for women/men) and have insomnia based on DSM-5 and research diagnostic criteria will participate in a randomized pilot trial. Participants will be randomly assigned to receive personalized normative alcohol feedback in the context of one of two treatment conditions: CBT-I (n = 22) or a sleep hygiene education control (SH; n = 22). Outcomes will be assessed at the end of the active intervention period (6 weeks), mid-treatment (after 3 sessions), post-treatment, and at 3 months post-intervention. Outcomes of interest include insomnia severity, total wake time, sleep quality, drinking quantity/frequency, alcohol-related consequences, executive functioning, negative affect, emotion regulation, craving for alcohol, and use of alcohol as a sleep aid.

2. Objectives (include all primary and secondary objectives)

- (1) To evaluate the feasibility and acceptability of CBT-I among heavy-drinking Veterans.

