- (2) To evaluate the effect of insomnia treatment on insomnia severity, total wake time, and sleep quality.
- (3) To evaluate preliminary treatment efficacy in reducing alcohol use, alcohol-related problems, and proposed mediators.

3. Background

Three out of four returning Veterans report heavy drinking in the context of poor sleep health (Swinkels, Ulmer, Beckham, Buse, & Calhoun, 2013). **The co-occurrence of these behaviors**, in combination with the anticipated stigma of mental health treatment (Vogt, Fox, & Di Leone, 2014), **represents a barrier to wellness among Veterans** (CDC, 2015; Fuehrlein et al., 2016). Symptoms of insomnia have been associated with elevations in alcohol use and related problems among returning Veterans (Luxton et al., 2011; [name], DiBello, Carey, & Pedersen, 2017; Swinkels et al., 2013). While the precise mechanisms underlying these associations are unclear, we propose four distinct pathways. First, insomnia has been associated with (1) deficits in executive functioning (Alhola & Polo-Kantola, 2007; Benitez & Gunstad, 2012; Fortier-Brochu & Morin, 2014), which may lead to poor decision-making and increased risk of alcohol problems (Day, Kahler, Ahern, & Clark, 2015). Insomnia symptoms have also been associated with (2) negative emotionality (Pickett, Barbaro, & Mello, 2015; Sandru & Voinescu, 2014), which may exacerbate alcohol problems in the context of heavy drinking (Watkins,

Franz, DiLillo, Gratz, & Messman-Moore, 2015), and (3) greater craving for alcohol (Mason, Light, Williams, & Drobis, 2009), which is a predictor of alcohol use (Bujarski & Ray, 2014). (4) Finally, insomnia may lead to use of alcohol as a sedative (Brower, Aldrich, Robinson, Zucker, & Greden, 2001).

[figure not shown]

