Insomnia Severity Index. The Insomnia Severity Index (Morin, Belleville, Belanger, & Ivers, 2011) will be used as a 7-item measure of insomnia severity in the past two weeks. Items assess difficulty falling or staying asleep, satisfaction with current sleep pattern, interference with daily functioning, the extent to which others notice their sleep problems, and worry/distress related to sleep problems. Response options range from 0 (not at all worried) to 4 (very much worried), with possible total scores ranging from 0 to 28. Participants scoring 10 or higher will be classified as screening positive for insomnia (Morin et al., 2011). Notably, self-report is the recommended method of assessment for symptoms of insomnia in adults (Schutte-Rodin et al., 2008).

Actiwatch 2. The Actiwatch 2 (Philips Respironics) is a watch-like device that monitors body movement. Actigraphy data will be used in conjunction with self-report data to estimate sleep onset latency, wake after sleep onset, and total sleep time. Data will be analyzed by proprietary software using 30s epochs. Actigraphy provides valid estimates of nighttime awakenings, wake after sleep onset, total sleep time, and sleep efficiency when compared to polysomnography (Kushida et al., 2001; Lichstein et al., 2006).

Daily Sleep Diary. The sleep diary used in this study includes all elements of the consensus sleep diary used in sleep studies across the nation (Carney et al., 2012). Participants will estimate what time they got into bed, what time they tried to go to sleep (bedtime), how long it took them to fall asleep (sleep onset latency), the total duration of nighttime awakenings (wake after sleep onset), the time of their final awakening (waketime), and what time they got out of bed for the day. Sleep onset latency and wake after sleep onset will be summed to

estimate total wake time. Total wake time will be subtracted from time in bed to estimate total sleep time. Participants will also rate sleep quality on a scale from 0 (very poor) to 4 (very good). Finally, they will be asked to report the number of standard drinks consumed; if they used alcohol (yes/no), marijuana (yes/no), or other illicit drugs (yes/no) to help with sleep; and the name, dose, and time of any sleep medication they used to help with sleep.

7b. Secondary Outcomes

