Data analysis. All questionnaire and behavioral task data will be scored according to published conventions. We will test for group equivalence in gender, age, race/ethnicity, use of sleep medication (# LRD), use of other drugs, and perceptions of peer drinking quantities (descriptive norms) at baseline. Group differences are unexpected in the context of randomization; however, if one of these variables is associated with both group and a given outcome variable, we will include it as a covariate in the prediction of that outcome. Data will be screened for integrity, outliers, missing values, and violations of the assumptions of MLM. Outliers will be replaced with the value that is 3 standard deviations +1 unit above the mean (Tabachnick & Fidell, 2007), and missing values will be handled in MLM using full maximum likelihood estimation.

Cohen's *d* and 95% CIs will be used to examine the magnitude of between-group differences mid-treatment, post-treatment, and at 1-month follow-up. We chose MLM over other statistical approaches because it requires fewer assumptions and has superior ability to handle missing data. In each model, the Level 1 variable will be time. Level 2 portions of the model will include the effect of condition and necessary covariates. The impact of CBT-I on insomnia symptoms will be tested by regressing condition on the Level 1 intercept and time effect. We will examine whether attrition is associated with any baseline variables and control for such variables when necessary. We will also explore CBT-I effects on alcohol use and proposed mediators, though we will be underpowered to detect small to moderate effects. We will use MLM to examine the within-individual associations between insomnia symptoms and alcohol use.

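### The diary total sleep time formula does not say which clock times bound time in bed; read literally, it counts waking minutes in bed as sleep

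*Combined protocol and SAP*

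**What the plan says.** Section 7a, Daily Sleep Diary, collects four clock times. The first two are introduced by "Participants will estimate what time they got into bed, what time they tried to go to sleep (bedtime", where bedtime is the plan's label for the sleep attempt and not for getting into bed. The last two are "the time of their final awakening (waketime), and what time they got out of bed for the day". The diary also records sleep onset latency and the total duration of awakenings during the night.

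Two derived quantities follow. For total wake time, "Sleep onset latency and wake after sleep onset will be summed to" give the estimate. For total sleep time, "Total wake time will be subtracted from time in bed to estimate total sleep time". The text does not link time in bed to any two of the four clock times. The phrase also appears in the CBT-I description in Section 4 and under fatigue in the Risks section, again without clock times.

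Objective 2 is "To evaluate the effect of insomnia treatment on insomnia severity, total wake time, and sleep quality". The Abstract's list begins in the same way: "Outcomes of interest include insomnia severity, total wake time, sleep quality". Neither list names total sleep time.

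**The concern.** The diary separates getting into bed from trying to sleep, and waking for the last time from getting up. The total sleep time formula does not use that separation. In ordinary use, time in bed means the whole span from getting in to getting out. The wake time subtracted from it covers only the stretch between the sleep attempt and the final awakening. Wakefulness at either end of the night therefore stays in the result as sleep.

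The later interval is plausible in this population, because Section 5 admits participants whose complaint is waking too early. What is at stake is the accuracy of a measure derived under Primary Outcomes. Its between-arm contrast is also at stake if the two end intervals change differently by arm. Section 4 describes CBT-I as including sleep restriction and stimulus control, both of which act on how long participants stay in bed, so the treatment may alter the intervals that the formula mishandles.

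**Working it through.** The plan gives no figure to reproduce. The check is an identity on the diary items in Section 7a.

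**Notation.** B = into bed; A = sleep attempt; W = final awakening; O = out of bed; L = sleep onset latency; K = wake after sleep onset; S = actual sleep. Let P = A − B and T = O − W.

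**Two assumptions, which the plan does not spell out.** Latency is counted from the sleep attempt, and wake after sleep onset stops at the final awakening. Both are the natural reading of the diary items. They give W − A = L + S + K.

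**Literal window (into bed to out of bed).**
(O − B) − (L + K) = (P + L + S + K + T) − (L + K) = S + P + T.
The result exceeds actual sleep by P + T.

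**Labelled window (sleep attempt to final awakening).**
(W − A) − (L + K) = (L + S + K) − (L + K) = S.
The result is exact for any P and T.

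**Numerical check of the identity.** All minutes here are assumed, and none comes from the documents. Take L = 45, K = 45 and S = 360, so W − A = 450 and total wake time = 90.

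| P | T | Literal window | Literal result | Excess | Labelled result |
|---|---|---|---|---|---|
| 0 | 0 | 450 | 450 − 90 = 360 | 0 | 450 − 90 = 360 |
| 15 | 15 | 480 | 480 − 90 = 390 | 30 | 360 |
| 30 | 45 | 525 | 525 − 90 = 435 | 75 | 360 |
| 60 | 60 | 570 | 570 − 90 = 480 | 120 | 360 |

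The rows confirm the algebra and show that the error can be nil. They do not estimate what this trial would see, and they are errors in level, not treatment effects.

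**Effect on the contrast.** Under the literal window, the error in the between-arm difference in change equals the between-arm difference in change of P + T. It is zero if the arms change equally.

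**Total wake time.** L + K contains none of B, A, W or O, so it is 90 minutes in every row whichever window is used.

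**The case against.** The strongest reply is that the plan's own labels point to the right window. Only two clock times carry a variable name: the sleep attempt (bedtime) and the final awakening (waketime). Subtracting wake time from the span between them gives no error, and the sponsor may well have meant that. This stands as a reason to treat the point as an ambiguous rule and not as a demonstrated miscalculation. It does not close the gap, because the formula uses neither label and its plain words describe a different span.

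A second reply is that Section 8 promises "All questionnaire and behavioral task data will be scored according to published conventions", and that Section 7a ties the diary's items to a cited consensus instrument. Whether questionnaire data includes the diary is arguable, and the cited source cannot be consulted here. Within the documents, no section fixes the window, and Section 7a states a formula of its own.

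A third reply is that actigraphy also supplies total sleep time: "Actigraphy data will be used in conjunction with self-report data to estimate sleep onset latency, wake after sleep onset, and total sleep time". That limits reliance on the diary value but does not replace or correct it.

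A reader might also pair two start times with two end times and infer that three of four windows go wrong, so that error is the likelier outcome. The algebra of that count is right, but nothing in the text suggests either mixed window. The realistic choice is between the literal window and the labelled one.

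**Conclusion.** The concern holds as a minor point. Followed literally, the formula overstates diary total sleep time by the minutes between getting into bed and trying to sleep, plus the minutes between the final awakening and getting up. The sleep attempt to final awakening window has no such error under the two assumptions stated above, but the plan does not name it.

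The size cannot be given, because the documents report no minutes for either interval. It is zero if both intervals are zero, and it drops out of the arm comparison if both arms change equally. Equal change cannot be assumed when one arm's treatment restricts time in bed.

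Two stronger readings are not supported. A reader might infer that the diary contrast is biased against CBT-I. That would require the two end intervals to shrink more under CBT-I than under sleep hygiene, and the documents do not establish this: less time in bed could also come from the stretch between sleep attempt and final awakening. A reader might also infer that total wake time is wrong. It is clearly defined and does not depend on the window.

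The weight is limited further because total sleep time, although derived under Section 7a, is absent from Objective 2 and from the Abstract's outcomes, and Section 8 specifies no test for it.

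**What to change.** In Section 7a, replace the total sleep time sentence with an explicit formula: (final awakening − sleep attempt) − sleep onset latency − wake after sleep onset. State that latency is counted from the sleep attempt and that wake after sleep onset ends at the final awakening. If the term time in bed is kept for any other derived quantity, name the two diary clock times that bound it. Leave total wake time as defined.

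The cost is a sentence or two of definition and the matching line in the scoring code. No new data are needed, because all four clock times are already in the diary. Diaries already collected can be rescored.

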Cognitive Behavioral Therapy (CBT-I) is the first line of treatment for insomnia (Rybarczyk, Lund, Mack, & Stepanski, 2009; Schutte-Rodin, Broch, Buysse, Dorsey, & Sateia, 2008; Siebern & Manber, 2011). It has moderate to large effects among Veterans, with improvements documented up to 6 months (between-group effect sizes=0.5-0.8; 10-11% more time asleep in bed at post-treatment and 6mo) (Edinger et al., 2009; Germain et al., 2014; Karlin, Trockel, Taylor, Gimeno, & Manber, 2013; Taylor et al., 2018). Research with college students (Fucito et al., 2017; Hershner & O'Brien, 2016) and animal models (Vengeliene, Noori, & Spanagel, 2015) suggests that improvements in insomnia may reduce heavy alcohol use, and pharmacological treatment of insomnia has been found to delay relapse among individuals with alcohol use disorder (AUD) (Anton et al., 2011; Brower et al., 2008). Based on this research, **CBT-I is expected to reduce insomnia symptoms among heavy-drinking Veterans**, thereby resolving insomnia-related deficits in executive functioning, negative emotionality, and craving for alcohol, as well as use of alcohol as a sleep aid. **These improvements, in turn, are expected to reduce alcohol use and related problems.** This line of research is particularly promising for Veterans, as Veterans generally perceive stigma toward mental health treatment (Vogt et al., 2014) but indicate interest in treatment for insomnia (Hom et al., 2016; Plach & Sells, 2013; Shepardson, Funderburk, Pigeon, & Maisto, 2014).

4. Study Procedures

This research will examine the efficacy of CBT-I in improving sleep and alcohol use outcomes among heavy-drinking OEF/OIF/OND-era Veterans. Forty-four Veterans will be randomized to receive sleep hygiene or to participate in five sessions of individual Cognitive Behavioral Therapy for Insomnia (CBT-I). Outcomes will be assessed at baseline, mid-treatment (3 weeks), post-treatment, and 3-month follow-up (see Figure 1).

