Penn Alcohol Craving Scale. The Penn Alcohol Craving Scale is a 5-item measure of alcohol craving in the past week. Participants rate the intensity, frequency, and duration of cravings, as well as their ability to resist acting on those cravings and their overall “average alcohol craving” for the past week. This measure has demonstrated good internal consistency and construct validity (Flannery, Volpicelli, & Pettinati, 1999).

8. Study Statistics

Power analysis. We chose to utilize G-Power, rather than a power analysis specific to multilevel modeling (MLM, sometimes referred to as mixed modeling) because powering for ANOVA will ensure we are adequately powered for MLM analyses, which will increase power to detect significant effects. Based on previous studies, the expected effect size is large for insomnia outcomes (based on trials with Veterans) (Germain et al., 2014; Talbot et al., 2014), medium for alcohol use outcomes (based on trials with college students) (Fucito et al., 2017), and medium for executive functioning outcomes (based on trials with fibromyalgia patients) (Miro et al., 2011). We used G-Power to determine the sample size needed for an a priori repeated measures ANOVA, within-between interaction ($\alpha = .05$, power = .95, groups = 2, repetitions = 4, correlation = .40). Based on these calculations, the sample size required to detect a small effect ($f = .10$) is 260; a medium effect ($f = .25$) is 44; and a large effect ($f = .40$) is 18. Assuming 2/month recruitment and 35% attrition, we plan to recruit 68

participants over 34 months to obtain a final sample of 44 participants. This will provide us with an adequate sample size to detect moderate to large group by time interactions.

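### Power for a 3-df ANOVA interaction does not guarantee power for the planned mixed-model test; the time coding is unstated, and under a slope in weeks a plateau lowers power for medium effects

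*Combined protocol and SAP*

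**What the plan says.** Section 8, Power analysis, sizes the trial on an "a priori repeated measures ANOVA, within-between interaction", with α = .05 and "power = .95, groups = 2, repetitions = 4, correlation = .40". It gives totals of 260 participants at f = .10 and 18 at f = .40. For the case that sets the trial's size, it states that the total for "a medium effect ($f = .25$) is 44". It expects large effects for insomnia and medium effects for alcohol use and executive functioning. It gives no separate calculation for the multilevel model, because "powering for ANOVA will ensure we are adequately powered for MLM analyses, which will increase power to detect significant effects".

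Section 8, Data analysis, makes time the Level 1 variable and tests the effect on insomnia symptoms by "regressing condition on the Level 1 intercept and time effect". It does not say whether time is in weeks, visit number, categories or pieces. Effects on alcohol use and the proposed mediators are to be explored, with an acknowledgement that power is lacking for small to moderate effects. Cohen's d with 95% confidence intervals is planned visit by visit.

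Table 1 puts the four assessments at weeks 1, 4, 6 and 20. Section 3, Background, cites between-group effects of 0.5-0.8 in Veterans and "10-11% more time asleep in bed at post-treatment and 6mo".

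**The concern.** The powered test and the planned test differ. A 3-df interaction responds to any pattern of group differences over four visits. A single condition-by-time coefficient responds only to the part of the pattern that lies along the chosen time scale. In calendar weeks the last visit stands far from the other three and dominates the slope. An effect gained by the end of treatment and then held, which is the shape the Background reports for time asleep in bed, is poorly described by a straight line over 19 weeks.

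Two things are at stake. The .95 power may not apply to the test that is run. And because the coding is open, the same data can be tested with quite different sensitivity according to a choice made later.

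**Working it through.** **Inputs.** From section 8: α = .05, 2 groups, m = 4 visits, ρ = .40, f = .10, .25 or .40, N = 260, 44 or 18. From the Abstract: 22 per arm. Visit times from baseline: either about 0, 3, 6 and 19 weeks (text: 3 weeks, 6 weeks, then 3 months) or 0, 3, 5 and 19 (Table 1, weeks 1, 4, 6, 20). Assumptions not in the documents: compound symmetry, complete data, and the shape of the group difference over visits. I use (0, .5, 1, 1) for a plateau from post-treatment and (0, 1, 1, 1) for an effect complete by mid-treatment.

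**1. The plan's own figure.** Noncentrality is λ = f²·N·m/(1 − ρ), with 3 and 3(N − 2) df.
- f = .25, N = 44: λ = .0625 × 44 × 4/.6 = 18.33; F(3, 126) power = .957.
- f = .10, N = 260: .951. f = .40, N = 18: .956.

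The stated sample sizes reproduce.

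**2. One slope instead.** With the same total effect, a 1-df linear-time test has λ_slope = λ·r², where r is the correlation between the centred effect pattern and the centred time codes.

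Example, pattern (0, .5, 1, 1) and weeks 0, 3, 6, 19:
- centred pattern (−.625, −.125, .375, .375), sum of squares .6875
- centred weeks (−7, −4, −1, 12), sum of squares 210
- cross-product 4.375 + .5 − .375 + 4.5 = 9.0
- r² = 81/(.6875 × 210) = .561, so λ_slope = 10.29

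Results at f = .25, N = 44 (42 error df; using 126 adds about 1 point at most):

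| Time code | (0, .5, 1, 1): r², power | (0, 1, 1, 1): r², power |
|---|---|---|
| 3-df ANOVA | .957 | .957 |
| Weeks 0, 3, 6, 19 | .561, .88 | .311, .65 |
| Weeks 0, 3, 5, 19 (Table 1) | .509, .85 | .286, .61 |
| Visits 0-3 | .891, .98 | .600, .90 |

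Simulated random-intercept mixed models (400 runs per cell) agree: .84 and .55 for the Table 1 weeks, .99 and .87 for visits 0-3.

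**3. The effect size expected for insomnia.** At f = .40, N = 44, λ = .16 × 44 × 4/.6 = 46.93. Over the two sets of weeks, the week slope has power above .99 for (0, .5, 1, 1) and .95-.96 for (0, 1, 1, 1).

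**4. What f means in SD units.** A plateau difference d gives f = (d/2)·√(SS/4), where SS is the pattern's sum of squares. For (0, .5, 1, 1), f = .25 needs d = .5/√(.6875/4) = 1.21; for (0, 1, 1, 1), 1.15. At f = .40 these are 1.93 and 1.85. The Background cites 0.5-0.8, taken here as SD units.

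**5. A named contrast.** For the baseline-adjusted difference at post-treatment, SE = √[(1 − ρ²) × 2/22] = √(.84 × .0909) = .276 SD, with 41 df.
- d = 0.5: noncentrality 1.81, power .42.
- d = 0.8: noncentrality 2.89, power .81.
- d = 1.2: power .99.

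For comparison, at d = 0.8 with pattern (0, .5, 1, 1) the ANOVA has power .64, the week slope .51-.55 and the visit-number slope about .75.

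**The case against.** The strongest reply is that the premise is inferred. The Data analysis section never uses the words linear, slope or weeks. If time is categorical, the group-by-time test is close to the one powered; if it is the visit number, a post-treatment plateau gives .98, above the ANOVA, and the plan's remark that the mixed model gains power is then right. This stands, and it makes the defect an unstated coding and an unsupported guarantee. It does not rescue the guarantee, which would have to hold under every coding left open; even visit-number coding drops to .90 for (0, 1, 1, 1).

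Second, the time-effect test is written for insomnia symptoms, where f = .40 is expected and a plateau costs little; alcohol and mediators are exploratory. This also stands. Two qualifications apply: f = .40 corresponds to about 1.9 SD on these patterns, well above the effects the Background cites, and the drinking and alcohol-consequence measures are nevertheless listed as primary outcomes in section 7a.

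Third, visit-specific Cohen's d would display an early effect, and full maximum likelihood uses partial data from dropouts. Both soften the consequence. As an upper bound, 68 complete cases would give the week slope (Table 1 weeks, post-treatment plateau) about .96.

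A reader might go further and suppose that the effect fades. If it halves by 3 months, the slope over weeks 0, 3, 6 and 19 has power of only .23 at f = .25. The documents do not support that shape: the Background reports improvements lasting up to 6 months.

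**Conclusion.** The sentence claiming that ANOVA power secures mixed-model power is wrong as a guarantee, and the planned test cannot be matched to a power figure until the coding of time is stated. Under a slope in weeks with a post-treatment plateau, the cost at f = .25 and N = 44 is about 8 to 11 percentage points (.957 to .85-.88). It is about 31 to 35 points if the effect is complete by mid-treatment, a shape on which the documents are silent. These figures rest on compound symmetry with ρ = .40, complete data and the assumed shapes; the plateau evidence concerns time asleep in bed only.

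A reader might infer that the plan commits to a linear slope in weeks, or that the insomnia comparison loses its power through the choice of model. Neither follows: week coding is one reading among several, and at the plan's own f = .40 the week slope keeps about .95 or more under a plateau. The loss falls mainly on the medium-effect outcomes. The scale of the assumed effect matters at least as much: at 0.5-0.8 SD with pattern (0, .5, 1, 1), the ANOVA itself has power of only .28-.64 with 44 participants.

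**What to change.** In Data analysis, model assessment as a categorical factor in the mixed model, with the baseline value as covariate, and name the condition contrast to be tested, for example at post-treatment, with 3 months also reported. In Power analysis, delete the sentence that ANOVA power ensures mixed-model power, and restate power for the named contrast in SD units. For the post-treatment contrast with 44 participants this is about .42 at 0.5 SD and .81 at 0.8 SD, with ρ = .40. Quoting .98-.99 for the same contrast would require a difference of about 1.2 SD and would replace one optimistic figure with another.

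The choice of post-treatment is a suggestion; what is needed is that one contrast be fixed before analysis. The change needs no new data or participants. It costs a few more fixed effects and a less favourable stated power.

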Follow-up assessments. To enhance follow-up rates, participants will receive up to \$300 for completion of all phases of this study. The proposed payment schedule is as follows:

Baseline		Up to \$70
Clinical interview (Zoom)	60-90min	\$0
Online survey	30-45min	\$30
14 days of actiwatch	---	\$20
14 consecutive diaries	2-3min/day	
-7 in a row to be eligible		needed for eligibility, \$0 bonus
-10 in a row		\$10 bonus
-14 in a row		\$20 bonus
Mid-Treatment		Up to \$20
Online survey	10-15min	\$20
Post-Treatment		Up to \$80
Online survey	30-45min	\$20
-phone only	5min	\$10
14 days of actiwatch	---	\$30
14 consecutive diaries	2-3min/day	

-7 in a row		\$10
-10 in a row		\$20
-14 in a row		\$30
3-Month Follow-Up		Up to \$130
Online survey	30-45min	\$50
-phone only	5min	\$20
14 days of actiwatch	---	\$40
14 consecutive diaries	2-3min/day	
-7 in a row		\$10
-10 in a row		\$20
-14 in a row		\$40

Participant retention. To enhance follow-up rates, participants will receive up to \$70 for completion of the baseline, \$20 for the mid-treatment assessment, up to \$80 for the post-treatment assessment, and up to \$130 for the 3-month follow-up; for a total of up to \$300. They will also receive reminder texts/calls, have access to free parking outside the research lab, receive immediate payment, and have access to after-hours ‘on-call’ support. We will also send all participants a personalized “thank you” note following study completion.

Blinding. [name] will not be blinded to block size or participant assignment because she will inform study therapists of participant assignment to conditions. However, [name] and study therapists will be blinded to assessment outcomes, and the assessment RA will be blinded to participant condition. All participants will be told that they are receiving treatment for insomnia in order to blind them to condition assignment (sleep hygiene will be described as “brief” insomnia treatment, and CBT-I will be described as the “most intense” treatment).

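### The one power calculation assumes four repetitions, but the detailed schedules give diary and actigraphy outcomes three, so at a medium effect N = 44 gives them about .91 power rather than .95

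*Combined protocol and SAP*

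**What the plan says.** Section 8 (Study Statistics, Power analysis) describes one G-Power run for an "a priori repeated measures ANOVA, within-between interaction", with alpha .05, power .95 and "groups = 2, repetitions = 4, correlation = .40". It reports 260 participants for a small effect (f = .10) and adds that the number for "a medium effect ($f = .25$) is 44; and a large effect ($f = .40$) is 18". From this it concludes that a final sample of 44 is adequate for moderate to large group-by-time interactions. The same paragraph says that "the expected effect size is large for insomnia outcomes (based on trials with Veterans"), and assigns a medium effect to alcohol use and executive functioning.

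Four repetitions match the general schedule at the start of section 4: baseline, mid-treatment, post-treatment and 3 months.

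Objective 2 in section 2 is "To evaluate the effect of insomnia treatment on insomnia severity, total wake time, and sleep quality". Section 7a takes total wake time and sleep quality from the daily sleep diary.

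The payment schedule in section 4 (Follow-up assessments) lists "14 consecutive diaries" and 14 days of actiwatch wear at baseline, post-treatment and 3 months. Its mid-treatment entry is a 10-15 minute online survey and nothing else. Table 1 agrees: the diary bonus appears at weeks 2, 7 and 21 only.

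The Coercion paragraph under Risks differs. It describes actiwatch and diary payments at baseline, post-treatment, one month and three months. A 1-month follow-up also appears in the Data analysis text of section 8 and in the note to Table 1.

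**The concern.** The number of repetitions enters the power formula directly, through the noncentrality parameter and both degrees of freedom. If an outcome is measured three times, a sample size worked out for four is too small for the same effect and power. Two of the three outcomes named in Objective 2 come from the diary, and all actigraphy measures follow the diary's schedule, so the mismatch reaches a good part of the outcome list. At stake is whether the printed sizes, and the statement that 44 suffices for moderate to large interactions, hold for those outcomes.

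**Working it through.** **Inputs.** From section 8, Power analysis: alpha = .05, target power .95, k = 2 groups, m = 4 repetitions, correlation rho = .40, f = .10, .25 and .40. From the abstract: equal groups, 22 + 22. Nonsphericity epsilon is not stated; 1 is assumed, and a range is shown below.

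**Formula.** For the within-between interaction:

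- lambda = f² × N × m × epsilon / (1 − rho)
- df1 = (k − 1)(m − 1) × epsilon
- df2 = (N − k)(m − 1) × epsilon
- power = P(noncentral F(df1, df2, lambda) > central F critical value at .05)

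N is stepped upward in equal groups until power reaches .95.

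**The plan's own figures, m = 4.** All three reproduce.

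| f | N | lambda | df1, df2 | Power |
|---|---|---|---|---|
| .10 | 260 | .01 × 260 × 4 / .6 = 17.33 | 3, 774 | .951 |
| .25 | 44 | .0625 × 44 × 4 / .6 = 18.33 | 3, 126 | .957 |
| .40 | 18 | .16 × 18 × 4 / .6 = 19.20 | 3, 48 | .956 |

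**The same inputs with m = 3.**

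| f | N | lambda | df1, df2 | Power |
|---|---|---|---|---|
| .25 | 44 | .0625 × 44 × 3 / .6 = 13.75 | 2, 84 | .914 |
| .25 | 50 | .0625 × 50 × 3 / .6 = 15.63 | 2, 96 | .946 |
| .25 | 52 | .0625 × 52 × 3 / .6 = 16.25 | 2, 100 | .954 |
| .40 | 18 | .16 × 18 × 3 / .6 = 14.40 | 2, 32 | .910 |
| .40 | 22 | .16 × 22 × 3 / .6 = 17.60 | 2, 40 | .960 |
| .40 | 44 | .16 × 44 × 3 / .6 = 35.20 | 2, 84 | .9998 |

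The sizes for .95 power therefore become 52 instead of 44 at f = .25, and 22 instead of 18 at f = .40. At f = .10 the figure is 312 instead of 260. With N = 44, the smallest effect detectable at .95 power is f = .27, against .246 with four repetitions.

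**Sensitivity at N = 44, m = 3.**

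| Assumption | f = .25 | f = .40 |
|---|---|---|
| rho = .2 | .813 | .997 |
| rho = .4 | .914 | .9998 |
| rho = .5 | .956 | above .999 |
| rho = .6 | .985 | above .999 |
| epsilon = .8 (rho = .4) | .861 | .999 |
| epsilon = .5 (rho = .4) | .726 | .984 |

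At f = .40, power stays above .95 throughout. At f = .25 it depends on the assumed correlation and sphericity at least as much as on the third versus fourth repetition.

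**The case against.** The strongest reply is that the plan expects a large effect for insomnia outcomes, and Objective 2 groups total wake time and sleep quality with insomnia severity. At f = .40 and three repetitions, 22 participants are enough and 44 give .9998. This stands. A reader might infer from the mismatch that the .95 power does not apply to total wake time or sleep quality; under the plan's own expected effect it does, with room to spare.

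A second reply is that the paragraph is a generic calculation, correct for its stated inputs, and that .914 is still adequate in the ordinary sense. The first part is true: there is no slip in the arithmetic. But the sample of 44 comes from the medium-effect calculation at .95, the adequacy claim extends to moderate interactions, and nothing limits it to outcomes with four assessments. The diary also records drinks consumed and alcohol used as a sleep aid. For an alcohol measure taken from it, the plan's expected effect is medium, so f = .25 with three repetitions is the relevant case. The consequence is limited, because the Data analysis text treats the alcohol effects as exploratory and concedes low power for small to moderate effects.

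Third, the gap of about four points lies within the uncertainty of the inputs: a correlation of .49 instead of .40 brings three-repetition power back to .952. The ANOVA is also only a stand-in for the planned multilevel model. Both points are fair and keep this minor.

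Fourth, the documents do not uniformly give three occasions. If the four in the Coercion paragraph are current, the stated figures hold for the diary and actigraphy outcomes too. Table 1 and the payment schedule are the more detailed sources and agree with each other, and the schedule at the start of section 4 has no one-month visit, so three is the better-supported reading. It is not certain.

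A reader might also look at a much smaller final sample, say 28, where three-repetition power at f = .25 is .73. That is mainly a sample-size matter: four repetitions would give only .81, and the plan treats 44 as the number left after attrition.

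**Conclusion.** The point holds in a limited form and is minor. On the detailed schedules, the printed sizes for .95 power are too small for diary and actigraphy outcomes: 52 rather than 44 at f = .25, and 22 rather than 18 at f = .40. With 44 participants, power at f = .25 is about .91 rather than .957, a loss of about four percentage points. This affects only the moderate end of the moderate-to-large claim for these outcomes. Power for total wake time and sleep quality at the large effect the plan expects remains above .99, and no larger sample is called for.

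The conclusion assumes three diary and actigraphy occasions, correlation .40, sphericity, equal groups, and the ANOVA as a proxy for the multilevel model. The documents do not say whether diaries are also kept during treatment, or which instruments the mid-treatment survey contains; the number of repetitions for each outcome therefore has to come from the investigators.

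**What to change.** Keep N = 44. First reconcile the assessment occasions across Table 1 and its note, the payment schedule, the Data analysis text and the Coercion paragraph. Then state in the Power analysis how many repetitions each outcome has. If the three-occasion schedule is confirmed, report power at N = 44 and f = .25 as about .95 for outcomes with four assessments and about .91 for diary and actigraphy outcomes with three, and add that power exceeds .99 at f = .40 in both cases. State the sphericity assumption alongside.

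The cost is a sentence or two and one slightly less favourable figure. Recruitment, conduct and analysis do not change.
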